4.7 BIOMARKER ANALYSES

For statistical modelling, raw concentration values of fluid biomarkers in their respective units will be log-transformed.

Change from Baseline in CSF mHTT Protein Level

The same MMRM model as for efficacy endpoints (see Section 4.4) will be used to model the change from baseline in mHTT (after log-transformation of mHTT). Results from the model will be back-transformed, in order to present model-based percent change in geometric means.

Due to data availability, the analyses of CSF mHTT protein level might not be completed by the time of the CSR writing so results of this analysis may be reported in an addendum to the CSR.

Annualised Percentage Change from Baseline in Whole and Regional Brain (Caudate, and Ventricular) Volume Measured by BSI, as Determined by Structural MRI

The same MMRM model as for efficacy endpoints (see Section 4.4), but without adjusting for baseline volume (as this is already taken into account by considering the percent change from baseline), will be used to model the annualized percent change from baseline in BSI, which means that the measured percent change from baseline to the analysis timepoint will be converted to reflect percent change from baseline normalized for the duration between baseline assessment and post-baseline assessment in years.

Change from Baseline in CSF NfL Protein Level

The same MMRM model as for efficacy endpoints (see Section 4.4) will be used to model the change from baseline in NfL (after log-transformation of NfL). Results from the model will be back-transformed, in order to present model-based percent change in geometric means.

4.8 EXPLORATORY HEALTH STATUS UTILITY ANALYSES

The exploratory health status utility endpoints are listed in Section 2.2.8.

Results for the exploratory health status utility endpoints will not be reported in the CSR.

4.9 SAFETY ANALYSES

Following the iDMC recommendation, effective 22 March 2021, no further study treatment was administered in this study. Patients in the study were continued to be followed for safety and efficacy outcomes until study completion.

All safety endpoints will be analyzed overall, i.e., disregarding if data was collected during on-treatment period or during off treatment follow-up period. On-treatment period is defined as time from first dose to last dose plus 5 months. Off-treatment follow-up period is defined as the time more than 5 months after last dose of study drug.

Analyses addressing the on-treatment period and off-treatment follow-up period are described in Section 5.

For all safety endpoints, if not stated otherwise, the baseline will be defined as the last assessment prior to the first lumbar puncture procedure or last assessment on Day 1, whichever occurred first.

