2.2.4 Safety Endpoints

- Incidence and severity of adverse events (AEs), with severity determined according to the Adverse Event Severity Grading Scale
- Change from baseline in Montreal Cognitive Assessment (MoCA)
- Change from baseline in vital signs
- Change from baseline in ECG parameters
- Change from baseline in clinical laboratory results
- Proportion of patients with suicidal ideation or behavior, as assessed by Columbia-Suicide Severity Rating Scale (C-SSRS) score at each visit, including

detailed focus on any individual cases identified as having severe ideation or behavior during the study conduct

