4.9.2 Adverse Events

All verbatim AE terms will be mapped to Medical Dictionary for Regulatory Activities (MedDRA) thesaurus terms and AE severity will be graded.

The incidence of AEs will be summarized on the basis of body systems and dictionary preferred terms and reported in individual listings and tables by treatment arm. The incidence of AEs by severity and relationship to study drug or study procedure and outcome will be provided.

The following AEs will be summarized by body system and preferred term:

- Any AE
- SAE
- AEs related to study treatment (any AE, SAE)
- AEs related to lumbar puncture
- AEs leading to discontinuation of study treatment
- AEs leading to dose modification or interruption
- AEs resulting in death
- Selected AEs

- Liver function
- Abuse potential
- Peripheral neurological events
- Central neurological events
- CSF proteins and leukocytes events
- Events potentially associated to brain ventricular expansion
- Renal function
- Thrombocytopenia
- Lumbar puncture associated (any time, occurring within 5 days)

The above mentioned summaries for AEs will be provided for AEs reporting during the on-treatment period. In addition, summary tables will be provided for on treatment AEs by ADA status, acknowledging that subgroups are defined by post-baseline data. AEs reported during the off-treatment period will be listed.

Adverse events are considered on-treatment if the AE onset date was before or at the date of last exposure to treatment plus 5 months, i.e., \leq last dose + 152 days.

Adverse events are considered post-treatment if the AE onset date was after the date of last exposure to treatment plus 5 months, i.e., $>$ last dose + 152 days.

In addition, COVID-19 related AEs will be summarized.

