5. ANALYSIS OF OFF-TREATMENT FOLLOW-UP DATA

Following the recommendation from the iDMC to halt dosing in Study BN40423, patients entered the off-treatment follow-up period to monitor their safety and efficacy endpoints after the treatment discontinuation. This section describes the statistical analyses that will use data collected after treatment termination.

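### SAP Section 4.9 promises an overall analysis of every safety endpoint, but 4.9.2 tabulates adverse events by arm only up to 152 days after last dose and merely lists later ones

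*SAP*

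**What the plan says.** All references are to SAP Version 3, the plan for the cohort enrolled under Protocol Version 4 and onwards, unless stated otherwise.

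The first safety endpoint in Section 2.2.4 is: "Incidence and severity of adverse events (AEs), with severity determined according to the Adverse Event Severity Grading Scale".

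Section 4.9 gives the general rule: "All safety endpoints will be analyzed overall, i.e., disregarding if data was collected during on-treatment period or during off treatment follow-up period". It ends the on-treatment period 5 months after last dose and then adds a pointer: "Analyses addressing the on-treatment period and off-treatment follow-up period are described in Section 5". Its baseline rule carries an exception clause: "For all safety endpoints, if not stated otherwise, the baseline will be defined as". The period rule carries none.

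Section 4.9.2 lists the AE summaries: any AE, SAEs, treatment-related and lumbar-puncture-related AEs, AEs leading to discontinuation or to dose change, AEs resulting in death, and selected AEs, which include events possibly linked to ventricular expansion. It then says: "The above mentioned summaries for AEs will be provided for AEs reporting during the on-treatment period". Events after that are treated differently: "AEs reported during the off-treatment period will be listed". The boundary is set by onset date: "Adverse events are considered post-treatment if the AE onset date was after the date of last exposure to treatment plus 5 months", which the section gives as 152 days.

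**The concern.** The two sections give different instructions for the same by-arm tables. Under 4.9, an SAE or death more than 152 days after last dose counts in its arm's incidence. Under 4.9.2 it does not, and the reader meets it only in a listing.

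This matters more here than in most trials. Dosing was halted after a safety review by the independent data monitoring committee, and patients were then followed off treatment, partly for safety. If late SAEs and deaths are only listed, nobody sees a by-arm count over the whole of follow-up, although 4.9 says the safety endpoints will be analyzed in that way.

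**Working it through.** No calculation decides this point, so the relevant texts are set against each other.

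1. **Is AE incidence covered by the general rule?** Yes. Section 2.2.4 lists it as a safety endpoint, and 4.9 applies to all safety endpoints.

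2. **Do different definitions of the period explain the difference?** No. Section 4.9 ends the on-treatment period 5 months after last dose. Section 4.9.2 uses the same limit and gives it as 152 days.

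3. **Does 4.9 leave room for an exception?** Not in its wording. The clause allowing for statements elsewhere is attached to the baseline definition, not to the period rule.

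4. **Does 4.9.2 present the on-treatment tables as an addition to overall tables?** No. Its additions are on-treatment tables by anti-drug antibody status and a summary of COVID-19 related AEs. Off-treatment AEs are assigned to a listing.

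5. **Does Section 5 supply the missing analysis?** No. It describes itself thus: "This section describes the statistical analyses that will use data collected after treatment termination". Its content is:
   - 5.1: repeated-measures models for cUHDRS, its components and MRI;
   - 5.2: slope models for cUHDRS, its components and MoCA;
   - 5.3: boxplots for ventricle volume, CSF protein and CSF leukocytes.

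   AEs appear in none of these. The only AE rule by period is the one in 4.9.2.

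6. **How far does the conflict reach?** It concerns AEs only. Sections 4.9.3 to 4.9.7 (laboratory data, vital signs and ECG, C-SSRS, MoCA, safety MRI) set no period restriction on their summaries, which is consistent with 4.9.

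**Worked case.** Take an SAE with onset 153 days after last dose. Under 4.9 it is in the by-arm SAE table. Under 4.9.2, since 153 > 152, it is post-treatment and is only listed. The safety population is the same under both rules (Section 4.1.2), so the denominator is unchanged and only the numerator differs.

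**Size.** The SAP gives no AE counts or rates for either period, so the difference in any table cannot be computed.

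**The case against.** The strongest reply is that the specific text governs the general. Section 4.9.2 is complete enough to program from: it names the tables, fixes the period and cut-off, and says what happens to later events. Section 4.9 is an umbrella sentence that fits the other safety subsections well. This largely stands. A programmer would probably follow 4.9.2, and the late events are not lost because they appear in a listing. What remains is that the AE output would then not deliver what 4.9 states, and the pointer to Section 5 leads to no AE analysis.

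A second reply concerns data collection. The only AE collection rule shown is footnote bb to the schedule of assessments in SAP Version 1, Appendix 2. It limits routine AE reporting to 5 months after the final dose. After that it covers all deaths, plus SAEs believed related to study drug of which the investigator becomes aware. That rule belongs to the superseded design, and the rule in Protocol Version 6 is not shown. If it was similar, the two readings would differ mainly in deaths and related SAEs. That narrows the point without removing it, since deaths and SAEs are the events for which a by-arm count matters most. Section 4.9.2 itself expects some off-treatment AEs to list.

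A reader might also infer more than the SAP supports:

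- **Weeks of AE data left out of the tables.** The window is 152/7 = 21.7 weeks. A patient with last dose at Week 53 who is followed to Week 101 has 101 − 53 − 21.7 = 26.3 weeks beyond it. That is calendar time, not AE data. Given the collection rule above, it does not measure how many events are omitted.
- **A choice left open to an unblinded sponsor.** Section 1 confirms that the sponsor was unblinded at the halt. But 4.9.2 is explicit, and nothing in the SAP suggests that its rule is optional or was chosen selectively.
- **Unequal follow-up for patients who stop early.** This is true of any on-treatment window. It is a separate matter of preference and does not follow from the contradiction.

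**Conclusion.** The inconsistency is real and minor. Section 4.9 requires an overall analysis of a set of endpoints that includes AEs, 4.9.2 tabulates AEs by arm for the on-treatment period only, and Section 5 does not fill the gap.

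On the assumption that 4.9.2 is followed, off-treatment SAEs and deaths, and any other late AEs collected, will be listed but not tabulated by arm. It should not be inferred that the AE tables are indeterminate or that late events are hidden: 4.9.2 can be programmed as written and calls for a listing. Nor can any shift in AE percentages be claimed. The effect depends on how many events began more than 152 days after last dose and on how completely they were collected, and the SAP shows neither.

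**What to change.** 1. Keep the on-treatment AE tables in 4.9.2 as they are.
2. Add to 4.9.2 overall by-arm summaries, covering on- and off-treatment events together, of at least SAEs, AEs resulting in death and selected AEs, from the data collected.
3. Amend 4.9 to say that the remaining AE summaries are on-treatment as set out in 4.9.2, and cite 4.9.2 beside Section 5 as a place where period-specific analyses are described.

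The cost is a few sentences and a few repeat runs of tables already specified. The overall tables should carry a note that AE collection more than 5 months after last dose may be less complete, so late non-serious events in particular should be read with caution.

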4.9.1 Exposure of Study Medication

Exposure to RO7234292 and placebo over the course of the study will be summarized using descriptive statistics for the safety evaluable population and the PK population. The duration of exposure, defined as number of days from first dose of study treatment to last dose plus 5 months (i.e., 152 days) as well as the duration of the off treatment follow-up period will be summarized descriptively.

4.9.2 Adverse Events

All verbatim AE terms will be mapped to Medical Dictionary for Regulatory Activities (MedDRA) thesaurus terms and AE severity will be graded.

The incidence of AEs will be summarized on the basis of body systems and dictionary preferred terms and reported in individual listings and tables by treatment arm. The incidence of AEs by severity and relationship to study drug or study procedure and outcome will be provided.

The following AEs will be summarized by body system and preferred term:

- Any AE
- SAE
- AEs related to study treatment (any AE, SAE)
- AEs related to lumbar puncture
- AEs leading to discontinuation of study treatment
- AEs leading to dose modification or interruption
- AEs resulting in death
- Selected AEs

- Liver function
- Abuse potential
- Peripheral neurological events
- Central neurological events
- CSF proteins and leukocytes events
- Events potentially associated to brain ventricular expansion
- Renal function
- Thrombocytopenia
- Lumbar puncture associated (any time, occurring within 5 days)

The above mentioned summaries for AEs will be provided for AEs reporting during the on-treatment period. In addition, summary tables will be provided for on treatment AEs by ADA status, acknowledging that subgroups are defined by post-baseline data. AEs reported during the off-treatment period will be listed.

Adverse events are considered on-treatment if the AE onset date was before or at the date of last exposure to treatment plus 5 months, i.e., \leq last dose + 152 days.

Adverse events are considered post-treatment if the AE onset date was after the date of last exposure to treatment plus 5 months, i.e., $>$ last dose + 152 days.

In addition, COVID-19 related AEs will be summarized.

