4.6 IMMUNOGENICITY ANALYSES

For the analysis, the following definitions based on Shankar et al. (2014) as well as a Sponsor's definition for ADA with neutralizing potential, will be used to describe patients' RO7234292 immunogenicity as follows:

- **ADA Negative**
 - ADA negative all samples: Patients who have no pre-existing ADA (i.e., antibodies reactive with the drug that are present in patients before treatment) or are missing ADA data before drug administration and who have all negative ADA results following drug administration, and treatment unaffected ADA-negative patients.
 - Treatment unaffected ADA: Subset of ADA negative patients who have pre-existing ADA but do not have a ≥ 4 fold increase in ADA titer following drug administration compared to baseline measurement.
- **ADA Positive**
 - Treatment induced: ADA developed de novo (seroconversion) following drug administration. Patients who have no pre-existing ADA or are missing ADA data before drug administration and who have at least one ADA positive sample following drug administration.
 - Treatment boosted: Patients who have pre-existing ADA and have a ≥ 4 fold increase in ADA titer following drug administration compared to baseline measurement.
- **Transient ADA**
 - Treatment-induced ADA detected only at one sampling time point during the on-treatment or off-treatment follow-up period (excluding the last sampling time point).
- **Persistent ADA**
 - Treatment-induced ADA detected at 2 or more sampling time points during the on-treatment or off-treatment follow-up period; or detected on last sampling time point.
- **ADA with Neutralizing Potential**
 - An ADA positive patient with declining or increasing PK based on visual assessment, and corroborated by PD markers.

Immunogenicity will be analyzed in patients included in the safety population who had at least one ADA assessment. Patients will be grouped according to treatment received or, if no treatment is received prior to study discontinuation, according to treatment assigned. The numbers and proportions of ADA-positive patients and ADA-negative patients at baseline (baseline prevalence) will be summarized by treatment group. For those who are ADA-positive, titers will be estimated as well as antibody subtype. In addition, the numbers and proportions of ADA-positive patients and ADA-negative

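### AE incidence by ADA status credits ADA-positive patients with events from before their first qualifying sample, and the plan acknowledges the post-baseline grouping without handling it

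*SAP*

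**What the plan says.** All references are to SAP Version 3.

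- **The table.** Section 4.9.2 plans AE summaries for the on-treatment period, with incidence as the stated measure, and adds that "summary tables will be provided for on treatment AEs by ADA status, acknowledging that subgroups are defined by post-baseline data".
- **ADA-positive.** Under Section 4.6 a treatment-induced positive is a patient with no pre-existing ADA, or with no baseline ADA data, "who have at least one ADA positive sample following drug administration". A treatment-boosted positive is defined by "Patients who have pre-existing ADA and have a ≥ 4 fold increase in ADA titer following drug administration compared to baseline measurement".
- **ADA-negative.** These are patients "who have all negative ADA results following drug administration, and treatment unaffected ADA-negative patients". A patient with pre-existing ADA and no 4-fold rise is therefore negative, even with positive samples.
- **Sampling period.** Persistent ADA is ADA "detected at 2 or more sampling time points during the on-treatment or off-treatment follow-up period; or detected on last sampling time point". The only entry condition is this: "Immunogenicity will be analyzed in patients included in the safety population who had at least one ADA assessment".
- **AE window.** Section 4.9 states: "On-treatment period is defined as time from first dose to last dose plus 5 months". Section 4.9.2 applies the same limit: "Adverse events are considered on-treatment if the AE onset date was before or at the date of last exposure to treatment plus 5 months". That is last dose plus 152 days.

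Section 4.9.1 summarizes duration of exposure, but not by ADA status. Section 4.9.2 does not say whether placebo patients enter the ADA tables.

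**The concern.** ADA-positive status is acquired after dosing starts, at whichever sample first qualifies. Whether an AE counts depends only on its distance from the last dose, never on that sample. This has two consequences.

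1. An AE in the first weeks is placed under ADA-positive even if the antibody is first detected a year later. Mixing in these events dilutes any real effect of ADA on safety.
2. A patient observed for longer has more chances both to qualify as ADA-positive and to have an AE. If sampling stops when observation stops, unequal follow-up alone can make the ADA-positive column look worse. Follow-up is unequal in this trial: Section 2.2 says that about 80% of participants had reached Week 69 when dosing was halted on 22 March 2021.

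The relationship between ADA status and safety is a listed exploratory outcome (Section 2.2.6). These tables are the only safety analysis that the SAP specifies for it.

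**Working it through.** The SAP states no figure on this point, so there is nothing to reproduce.

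**Inputs from the SAP:** the ADA definitions (4.6), the AE window of last dose + 152 days (4.9, 4.9.2), and the 80% at Week 69 (2.2). **Assumed, because the SAP does not give them:** samples at Weeks 5 and 13 and then every 8 weeks, the distribution of seroconversion times, the AE rates and the spread of last-dose dates.

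**Step 1: share of a patient's AEs before the first positive sample.** With a constant AE rate, the share is the time to the first positive sample divided by the AE window. For a last dose at Week 69, the dose falls on Day 1 + 7 × 68 = 477, and the window ends on Day 477 + 152 = 629.

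| First positive sample | Days since first dose | Share of window |
|---|---|---|
| Week 13 | 7 × 12 = 84 | 84/629 = 13% |
| Week 37 | 7 × 36 = 252 | 252/629 = 40% |
| Week 69 | 7 × 68 = 476 | 476/629 = 76% |

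If off-treatment samples count and the first positive falls after the window, the share is 100%.

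**Step 2: average over seroconversion times.**
- Last dose at Week 69, exponential seroconversion with medians of 60, 120, 240 and 480 days: 18%, 27%, 34% and 38%. Uniform over the dosing period: 42%.
- The same with the AE rate tripled in the first 90 days, medians of 120, 240 and 480 days: 40%, 47% and 50%.
- A second model has 15% early stoppers, other last doses on Day 400 to 690, sampling to the end of the AE window, 20% ADA-positive and 0.5 AEs per year. It gives 50% with a low constant ADA hazard, and 17%, 27% and 38% with medians of 60, 120 and 240 days.

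**Step 3: incidence with no ADA effect.** Patients were simulated with an AE hazard independent of ADA, sampling up to the last dose, and 10%, 30% or 60% AE incidence over 629 days.

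| Spread of last dose | Ever ADA-positive | Incidence ratio, positive/negative |
|---|---|---|
| All Week 69 | 28% to 94% | 1.00 to 1.01 |
| 80% Week 69, 20% Weeks 37 to 61 | 27% to 92% | 1.01 to 1.06 |
| 80% Weeks 69 to 93, 20% Weeks 5 to 61 | 29% | 1.08 to 1.09 |
| same | 50% | 1.11 to 1.13 |
| same | 73% | 1.18 to 1.23 |
| same | 90% | 1.42 to 1.55 |

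One example from the 73% row is 32.0% against 26.3%, a ratio of 1.22, with mean windows of 682 and 550 days. In the second model of Step 2 the excess is about 3 points with constant hazard and 0.3, 0.9 and 1.7 points with medians of 60, 120 and 240 days. If every patient is sampled to Day 800 whatever the AE window, the excess is 0.0 to 0.1 points, although the pre-positive share under constant hazard then rises to 56%.

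**Step 4: what the candidate remedies do.** With no ADA effect and the AE rate tripled in the first 90 days:
- the planned incidence table gives a ratio of 1.00 to 1.04;
- classifying each AE by ADA status at onset, without regard to time on study, gives a rate ratio of 0.78 to 0.81, because all early time is ADA-negative.

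Rates per person-time by ever-positive status give a null ratio of 0.99 to 1.00.

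**The case against.** The strongest reply is that the SAP discloses the limitation in the sentence itself. The tables are additional and descriptive, with no test or decision rule, and AEs are also listed individually, so onset order can be examined case by case. This stands, and it sets the severity. It does not remove the point, because the acknowledgement changes nothing in how events are counted.

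Four stronger readings are tempting, and the SAP does not support them.

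- A reader might infer that about half of the AEs in the ADA-positive column predate the antibody. That follows only from late or constant-hazard seroconversion, or from front-loaded AEs. Earlier seroconversion gives far less, and the SAP supplies nothing to choose between them.
- A reader might infer that the table must show an excess when ADA does nothing. With equal follow-up it does not. Section 4.6 also refers to off-treatment samples, and if early stoppers go on being sampled, the excess nearly vanishes.
- A reader might take a single positive sample as always sufficient. It is not for patients with pre-existing ADA.
- A reader might conclude that reclassifying AEs by status at onset is a complete cure. Without stratifying by time on study it can suggest protection of about 20% that is not real (Step 4).

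**Conclusion.** The point holds in a limited form. Crediting AEs from before the first qualifying sample to ADA-positive patients follows directly from Sections 4.6 and 4.9.2 and needs no assumption about follow-up. The inflation of crude incidence is conditional: it requires follow-up to differ between patients and ADA sampling to end with it.

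Size rests wholly on assumptions about seroconversion, sampling and AE timing. Roughly 17% to 50% of ADA-positive patients' AEs may predate the first positive sample, and somewhat more if sampling runs well past the AE window. With no ADA effect the excess is from about 0 to a few percentage points. Ratios near 1.5 arise only with widely spread follow-up and about 90% of patients ever positive, where the negative group is small and made up largely of early stoppers.

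Severity is low: a desirable improvement to an exploratory safety display. No efficacy or confirmatory conclusion depends on it.

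**What to change.** Keep the planned table in Section 4.9.2 and add two items.

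1. **Person-time and rates.** Within each active arm, give patient-years in the on-treatment window and AEs per 100 patient-years by ADA status, beside the percentages.
2. **Onset order.** Tabulate on-treatment AEs by onset before, or on or after, the first qualifying ADA sample. That is the first positive sample for treatment-induced ADA, and the first sample with at least a 4-fold titer rise for treatment-boosted ADA. Compare rates within intervals of time since first dose that are fixed in advance, so that early AEs are not automatically assigned to ADA-negative time.

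State also whether samples taken after the AE window can make a patient ADA-positive for these tables, and whether placebo patients appear in them.

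The cost is a little more programming from sample, dosing and AE onset dates already held. One limitation remains: detection lags true seroconversion by up to one sampling interval, so some events counted as before the first qualifying sample will in fact follow seroconversion.
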